1.0 Objectives

1.1 Study Objectives

OBJECTIVE 1. Partnering with 14 PA public high schools (letters of commitment obtained for all 14 high schools) serving an estimated 12,582 predominantly minority, rural, urban, and/or low socioeconomic status (SES) students, we will conduct a randomized controlled trial, with student randomization by grade, to compare the effectiveness of universal school-based screening for adolescent major depressive disorder (MDD) versus the existing process of targeted screening based on concerning behavior.

- *Hypothesis 1: Universal screening will increase the number of adolescents with MDD screened, identified and engaged in treatment (MDD composite).*
- *Hypothesis 2 (Moderating): Universal screening will increase the historically poorer rates of MDD screening, identification and treatment engagement for females*
- *Hypothesis 3 (Moderating): Universal screening will increase the historically poorer rates of MDD screening, identification and treatment engagement for rural adolescents*

OBJECTIVE 2. Analyze the impact of MDD screening on secondary outcomes currently collected by the school's Student Assistance Program (SAP) and the school district. These data will be obtained in aggregate by grade level at each participating school (a total of 64 data points for each item; 4 grades x 14 schools, see note below re: PCORI). Please note, secondary outcomes may no longer be available due to COVID-19 school closures and cancellation of state standardized testing.

- *Hypothesis 1. Standardized test scores (e.g. Keystone exams, PSAT, SAT, ACT) will improve in school populations with universal MDD screening secondary to earlier identification, treatment referral and engagement.*
- *Hypothesis 2. Student school policy violations and suspensions will remain unchanged among school populations with the universal MDD screening approach.*

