7.2.2 Randomization

We will randomize by grade levels within each school to receive either one-time universal screening (via PHQ-9) or targeted screening (current SAP process). For the schools included in the study, half of the schools (50%) will be randomized such that students in 9th and 11th grades will receive universal screening and students in 10th and 12th grades will receive targeted screening, and the other half (50%) will be randomized such that students in 9th and 11th grades will receive targeted screening and students in 10th and 12th grades will receive universal screening. Randomization will be done only for students whose parents do not signal an unwillingness to participate in the study (“opt out”). Students and study personnel will not be blinded to randomized group at each school site. Randomization will be done by grade level primarily for pragmatic reasons because many PA health-based screenings are grade-specific (e.g. hearing screen in 11th grade) and screenings for a grade occur at the same time. The study will be conducted within schools, but it is not a cluster randomized study, in which an entire school (cluster) is assigned to one of the study groups. A cluster randomized study was considered but ultimately not pursued because randomization within schools controls for (1) within-school (community) factors that may contribute to higher or lower rates of SAP referral, (2) differences in school sizes, and (3) potential differences in rates of parental opt out among schools. These benefits were balanced against the concern of potential contamination between study groups, whereby those in the targeted screening group may benefit from the school-wide push to conduct universal screening.

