8.0 Subject Numbers and Statistical Plan

8.1 Number of Subjects

The 9 HRSA funded schools to be included in the study have an estimated total enrollment of approximately 3,900 students (the PCORI funded urban schools have a total enrollment of approximately 8,150 students). The overall rate of parental opt out is expected to be around 20%,

resulting in approximately 9,640 students included in the study. We assumed a 15% attrition rate for students who move, drop out of school, or opt out later in the school year. This number will be finalized once we have a final confirmed list of participating schools. However, as the total number of students is greater than that originally projected below, the sample size determination section will be unchanged.

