8.3 Statistical methods

The principles of intention-to-treat (ITT) will be used for all statistical analyses related to primary and secondary aims. For the primary aim comparing universal to targeted screening, the statistical analysis will be conducted using a mixed effects logistic regression model. The primary outcome, MDD composite, will be an indicator whether a student was screen positive (or concerns raised in the targeted screening arm), identified as having MDD and subsequently engaged in treatment (1=yes, 0=no). The model will include a fixed effect for randomized group (0=targeted screening, 1=universal screening) and a random effect for school. The random effect accounts for correlation among students enrolled within the same school. The primary parameter of interest will be the log odds of MDD composite in the universal screening group compared to the targeted screening group. Statistical significance of the log odds will be assessed using a 2-sided Wald test. Point estimates for the odds ratio along with a 95% confidence interval will be reported.

For the analysis of Hypotheses 2 and 3 (Objective 1) evaluating universal screening and targeted screening by selected subgroups, the same mixed effects logistic regression modeling framework will be used, but the model will be extended by including a fixed effect for subgroup and an interaction effect for subgroup by randomized group. The interaction term will be the parameter of interest. A significant interaction term indicates that rates of MDD treatment engagement for universal versus targeted screening differ by subgroup level (e.g. female vs. male). For the secondary analyses (Objective 2) that evaluates universal screening and targeted screening based on school SAP data, we will have only 64 total data points (4 grades in each of the 14 schools). Mixed-effects linear (continuous outcomes) and logistic regression (binary outcomes) will be used, as appropriate, with a fixed effect for randomized group and a random effect for school. The parameter of interest will be the log odds for the universal compared to the targeted screening group. Due to the smaller sample size used for these outcomes, these analyses will be considered to be primarily hypothesis-generating. Potential mediating variables (socioeconomic status, ratio of guidance counselors to students and availability of school-based mental health services) will be evaluated for both the Objective 1 and 2 hypotheses.

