Additional secondary outcomes will include MDD screen results, MDD concern prompting Student Assistance Program triage, MDD identification and MDD treatment engagement analyzed individually (rather than as part of MDD composite). Finally any suicidal adolescents (suicidal thoughts [positive response to PHQ-9 item 9], attempts and completed) will be analyzed as a secondary outcome.

We need to collect data for individuals for 3 main reasons. First, we expect approximately 20% of students to opt out from the study, with opt out rates varying by grade. Aggregate data would necessarily include outcomes for students who are not enrolled in the study. This is particularly problematic for the universal screening group because students who opt out will not be offered the depression screening tool (PHQ-9). Second, we need to obtain gender and race/ethnicity to conduct important planned secondary analyses (subgroup analyses) that will examine efficacy of universal screening by these groups. In particular, we expect that females and minority students will have much higher rates of major depression disorder identified in the universal screening group. Third, in the

universal screening group, we will be able to link responses to the PHQ-9 to outcomes, which will allow for estimation of important measures such as the false positive rate of the PHQ-9 (score ≥ 11 , but SAP process determines no further referrals are needed). These measures will inform decision-making regarding the potential for implementation of the intervention (in other schools) should the results of the trial ultimately show efficacy.

Efforts will be made to ensure completeness of data where possible, but missing data will occur for a number of anticipated reasons. First, a student may move during the course of the school year to another school district or drop out from school entirely. No data will be collected after this time point. Second, parents may opt out their child from the study at any time during the school year. Third, students who turn 18 during the school may decide to opt out of the study themselves. In both of these instances, data from SAP referrals that occur after opting out will not be collected for purposes of the study. Fourth, during the one-time universal screening phase, students may decide to leave data forms incomplete, including the PHQ-9. To decrease these instances, the PHQ-9 will be taken on an iPad program and the survey will alert if the form is left incomplete.

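### The Objective 1 models leave out grade, the unit of allocation, so a chance imbalance between grade patterns goes unadjusted: minor for the primary odds ratio, of more concern for the rural-by-arm test (Hypothesis 3)

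*Combined protocol and SAP*

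**What the plan says.** All references are to the current protocol, the second of the two in the combined document.

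- **Allocation (section 7.2.2).** Arms are assigned to grade pairs within each school: "half of the schools (50%) will be randomized such that students in 9th and 11th grades will receive universal screening", and the remaining half get the reverse. The stated balance is in the number of schools. Nothing is said about balancing students, school size or rural/urban status.
- **Primary model (section 8.3).** "The model will include a fixed effect for randomized group (0=targeted screening, 1=universal screening) and a random effect for school".
- **Hypotheses 2 and 3 (section 8.3).** "the model will be extended by including a fixed effect for subgroup and an interaction effect for subgroup by randomized group". Hypothesis 3 in section 1.1 concerns "historically poorer rates of MDD screening, identification and treatment engagement for rural adolescents", and section 1.3 classifies students as rural or urban by their school district.
- **Other covariates (section 8.3).** "Potential mediating variables (socioeconomic status, ratio of guidance counselors to students and availability of school-based mental health services) will be evaluated". Grade is not among them.
- **Numbers (section 8.1).** "The 9 HRSA funded schools to be included in the study have an estimated total enrollment of approximately 3,900 students", and "the PCORI funded urban schools have a total enrollment of approximately 8,150 students".
- **Grade in the data.** Section 7.2.1 puts grade in the study ID and in the de-identified list sent to the study team. Section 8.3 adds: "we expect approximately 20% of students to opt out from the study, with opt out rates varying by grade".

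**The concern.** Within any one school, the comparison of arms is also the comparison of grades 9/11 with grades 10/12. A random school effect cannot remove a contrast that lies inside the school. Only the reversal between schools does so, and for the overall odds ratio it cancels a common grade difference only if the two patterns hold equal numbers of students.

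Hypothesis 3 is more exposed. If exactly half of all schools take each pattern, an excess of one pattern among urban schools forces the opposite excess among rural schools. The rural-by-arm term is the difference between the two, so the imbalances add.

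This is separate from residual correlation among students of the same grade and school. Here the issue is a grade difference common to all schools, which enters the point estimate and which the reported standard error does not reflect.

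**Working it through.** **1. The plan's own figure.** Students: 0.8 × (3,900 + 8,150) = 9,640, or 4,820 per arm. For 3% v 6%, the difference over its standard error is 0.03 / √[(0.03×0.97 + 0.06×0.94)/4,820] = 7.1, so power exceeds 99% as stated. The planned odds ratio is (0.06/0.94)/(0.03/0.97) = 2.06.

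**2. School sizes.** Rural: 3,900/9 = about 433. The number of urban schools is not given. Section 1.1 has 14 schools in total, which leaves 5 urban (8,150/5 = 1,630 each). Section 7.1 has 3 + 13 = 16, which leaves 7 (about 1,164 each). Nine, five and seven are all odd, so neither type can be split evenly under either total.

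**3. Formulas.** Let δ be the log odds ratio for grades 9/11 v 10/12. Let I be the share of students in one pattern minus the share in the other.
- Shift in the primary log odds ratio ≈ δ × I
- Shift in the rural-by-arm log ratio of odds ratios ≈ δ × (I_rural − I_urban)

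**4. Possible splits.** Assumptions: 9 + 5 schools, equal sizes within type, a random 7:7 split not stratified by type. Probabilities are hypergeometric. Each row includes its mirror image.

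| Rural / urban split | Probability | abs. I overall | abs. (I_rural − I_urban) |
|---|---|---|---|
| 5:4 / 2:3 | 73% | 0.099 | 0.311 |
| 6:3 / 1:4 | 24% | 0.298 | 0.933 |
| 7:2 / 0:5 | 2% | 0.497 | 1.556 |

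First row: I_rural = 1/9 = 0.111 and I_urban = −1/5 = −0.200. The difference is 0.311, and overall I = (0.111×3,900 − 0.200×8,150)/12,050 = −0.099.

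**5. Size of the shift.** No grade effect is given, so it is assumed. At 1.3, the primary odds ratio is multiplied or divided by 1.03, 1.08 or 1.14 in the three splits, and the Hypothesis 3 ratio by 1.09, 1.28 or 1.50. Under a steady trend the pair contrast is one grade step, so 1.1 implies 1.1³ = 1.33 from grade 9 to grade 12, 1.3 implies about 2.2, and 1.5 about 3.4.

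**6. Standard errors.** With the 15% attrition of section 8.1, n = 0.85 × 4,820 = 4,097 per arm. SE = √[1/(n×0.06×0.94) + 1/(n×0.03×0.97)] = 0.113. Dividing n in the ratio 3,900:8,150 gives 0.198 (rural) and 0.137 (urban), so the interaction SE is √(0.198² + 0.137²) = 0.241.

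**7. Effect on inference.** Normal approximation, averaged over the splits in step 4:

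| Assumed grade odds ratio | Primary 95% coverage | Actual size of the 5% Hypothesis 3 test |
|---|---|---|
| 1.1 | 94.7% | 5.6% |
| 1.2 | 94.0% | 7.3% |
| 1.3 | 92.8% | 9.7% |
| 1.5 | 89.7% | 16% |

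With 7 urban schools and an 8:8 split, primary coverage is 94.9%, 94.5%, 94.0% and 92.6%.

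**8. Does adding grade repair it?** Logistic fits to expected counts, with school intercepts standing in for the random effect, returned the true values (odds ratio 2.064, rural-by-arm ratio 1.000) in every split checked once grade was included. Arm stays estimable because the pattern is reversed between schools.

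**The case against.** The strongest case against has four parts.

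- **It is not bias in the usual sense.** The pattern is randomised to schools, so the expected shift is zero. That stands. This is chance imbalance, conditional on the realised split. But the trial has only one split, and the model standard error does not include the variation between splits.
- **The grade effect is unknown.** Nothing in the documents says that the composite outcome differs between 9/11 and 10/12. The remark on opt-out concerns enrolment, not outcome. Alternating grades also keep the contrast small under a steady trend. At 1.1 almost nothing happens. This stands, and it is why the result is a range and not an estimate.
- **Randomisation may have been stratified.** The rural and urban projects are funded separately, and schools start in two different years. The documents do not say whether either was a stratum. If rural and urban schools were randomised separately, the odd counts still leave at least 11% imbalance in the rural group and 20% in the urban group (5 schools), but the lopsided splits would be avoidable. Enrolments are also provisional.
- **Hypothesis 2 is hardly touched.** Both sexes attend every grade, so a common grade effect largely cancels from the sex-by-arm term. This stands.

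A reader might infer that arm is confounded with grade and that the primary result is unsafe. The documents do not support that. The reversed pattern separates arm from grade, power at the planned odds ratio of 2.06 exceeds 99%, and the most likely split moves that ratio by a factor of about 1.03 even at an assumed grade odds ratio of 1.3.

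**Conclusion.** The omission is certain: no Objective 1 model contains grade, although grade pair is what was allocated and grade is collected with the other demographic data. Its size is not certain. It rests on an assumed grade odds ratio, equal school sizes within type, 5 or 7 urban schools and an unstratified half-and-half split.

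Within those assumptions the effect on the primary odds ratio is minor. The main concern is Hypothesis 3. Its shift on the log scale is about 3.1 times the primary shift (0.311/0.099), its standard error is about twice as large, and its test exceeds the nominal 5% noticeably once the grade odds ratio reaches 1.2 or more. The conclusion is the same for 14 and for 16 schools. The change should be made because following the plan as written leaves an avoidable source of error out of the reported interval and test.

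**What to change.** In section 8.3, add grade (9, 10, 11, 12) as a fixed factor to the primary model, the Hypothesis 3 model and the individual-level secondary models. Add it to the Hypothesis 2 model for consistency only, as little change is expected there. Report the number of students per pattern, overall and by rural/urban. State whether randomisation was stratified, and reconcile the 14 and 16 school totals.

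The Hypothesis 3 correction assumes a similar grade effect in rural and urban schools. A sensitivity analysis with a grade-by-rural term can be run where it is estimable. It is not estimable if all urban schools share one pattern.

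**Cost:** one sentence in the plan and three degrees of freedom. In simulation the primary SE rose from about 0.113 to 0.116. The Hypothesis 3 SE goes from about 0.241 to 0.244 in the most likely split, to about 0.27 in the next, and to about 0.44 in the rarest. The larger costs fall in the lopsided splits, which are also those where the unadjusted estimate is most exposed.

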1.3 Secondary Study Endpoints

The secondary endpoints listed below are individual level data points that will be obtained from the school district and/or SAP. No identifiable information will be collected by study staff.

MDD screen positive or MDD concern prompting Student Assistance Program triage

Universal screening arm: Adolescents who have a PHQ-9 score ≥ 11 (screening with the PHQ-9 is planned for September to March) or who at any point in the school year exhibit behavior concerning for MDD which prompts self or collateral request for SAP triage.

Targeted screening arm: Adolescents with behavior concerning for MDD which prompts self or collateral request for SAP triage at any point during the school year.

Suicidal adolescent (includes suicidal thoughts [positive response to PHQ-9 item 9], attempts and completed)

Universal screening arm: Patient health questionnaire positive response to question #9 re: suicidal thoughts, which requires management by the state-mandated school crisis plan or student self or collateral report of suicidal thoughts, which requires management by the state-mandated school crisis plan (source school district).

Targeted screening arm: Student self or collateral report of suicidal thoughts, which requires management by the state-mandated school crisis plan (source school district).

Any student suicide attempts or completed suicides shared with the school district will also be included.

MDD identification

Universal and targeted screening arms: Adolescents who are identified as having MDD based on triage by the school SAP team. As SAP triage is not diagnostic, MDD identified will be based on SAP recommendations for school or community services which are MDD related (e.g. mental health treatment services).

MDD treatment engagement

Universal and targeted screening arms: Adolescents who successfully engage with at least one SAP recommendation. This may be fulfilled by parental report that an appointment was successfully scheduled

The secondary endpoints listed below are aggregate data points by grade level that will be obtained from the school district and/or SAP. No identifiable information will be collected by study staff. Please

note, secondary outcomes may no longer be available due to COVID-19 school closures and cancellation of state standardized testing.

Standardized test scores (i.e. Keystone exams, PSAT, SAT/ACT)
Student school policy violations and/or suspensions
Missed school days
Grade point averages

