Grade advancement or graduation rates

Additional data points to be obtained for subgroup analyses include:

- At the individual level:
 - Sex - male or female
 - Ethnicity - Hispanic vs. non-Hispanic
 - Race - white, black or other
 - Urban/rural – students will be categorized as enrolled in urban or rural school districts based on the definition applied by The Center for Rural PA, a Legislative Agency of the PA General Assembly for the district

- At the aggregate level, the following variables will be collected:
 - District socioeconomic status
 - School size – school enrollment. Data will be obtained from school districts based on enrollment as of October 1 of the RCT
 - Ratio of guidance counselors/students – The ratio of counselors to students will be obtained from each school district
 - School-based mental health services – schools will be categorized by the availability of school-based mental health services (yes vs. no) based on information obtained from each school district.

We need to collect data at the individual level for 3 main reasons. First, we expect approximately 20% of students to opt out from the study, with opt out rates varying by grade. Aggregate data would necessarily include outcomes for students who are not enrolled in the study. This is particularly problematic for the universal screening group because students who opt out will not be offered the depression screening tool (PHQ-9). Second, we need to obtain gender and race/ethnicity to conduct important planned secondary analyses (subgroup analyses) that will examine efficacy of universal screening by these groups. In particular, we expect that females and minority students will have much higher rates of major depression disorder identified in the universal screening group. Third, in the universal screening group, we will be able to link responses to the PHQ-9 to outcomes, which will allow for estimation of important measures such as the false positive rate of the PHQ-9 (score ≥ 11 , but SAP process determines no further referrals are needed). These measures will inform decision-making regarding the potential for implementation of the intervention (in other schools) should the results of the trial ultimately show efficacy.

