7.0 Study Design and Procedures

7.1 Study Design

Due to the timeline for this funding opportunity, with an anticipated July 2018 start, 3 schools will engage in the randomized control trial (RCT) in study year 1 and the additional 13 schools in study year 2. Many large scale randomized control trials do not enroll all participants at one time point, and in many cases enrollment occurs slowly over the course of several years. We do not anticipate there will be major changes over the course of two academic years that would significantly alter the results compared to conducting the RCT in the same academic year, especially because students will be randomized within schools. Finally, staggering enrollment will give the research team the opportunity to troubleshoot any unanticipated issues with the first 3 participating schools. The intervention ended early in study year 2 (March 2020) due to the COVID-19 pandemic and schools subsequently ending in-person instruction.

The study team was unable to complete PHQ-9 screeners with two participating schools [REDACTED]. SAP outcome data will still be collected for all enrolled students (i.e., those whose parents did not return the opt-out form) for the 2019-2020 (study year 2) school year. At the completion of the year one screener/ screening process, school staff will be asked to complete the Final Feedback Guide document to assist in our research/ knowledge of the study process and procedures. Staff members from two schools completed the Feedback Guide interview [REDACTED] as a pilot to ensure the final version of the Feedback Guide was thorough and comprehensive.

At the completion of the of the 2019/2020 school year, the 3 schools that participated in the RCT during the 2018/2019 school year, will be asked to complete the Year 2 feedback guide interview document to assist in our research/knowledge of the long-term feasibility and sustainability of study processes and procedures. During their second year of study participation, school participants will be asked to complete the feedback guide interview with research personnel. Due to the COVID-19 pandemic occurring during the 2019-2020 school year, we have added questions relevant to student mental health concerns.

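### Objective 2: a logistic model on grade totals with only a school random effect leaves out the randomized grade, and one log-odds parameter does not fit all the aggregate outcomes

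*Combined protocol and SAP*

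**What the plan says.** All references are to the current protocol version. Section 1.1 says of the Objective 2 outcomes: "These data will be obtained in aggregate by grade level at each participating school". Section 1.3 repeats this ("The secondary endpoints listed below are aggregate data points by grade level that will be obtained from the school district and/or SAP") and lists, among others, "Student school policy violations and/or suspensions" and "Grade advancement or graduation rates". It does not say whether violations and suspensions come as counts, rates or shares of students.

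Section 8.3 gives the analysis: "Mixed-effects linear (continuous outcomes) and logistic regression (binary outcomes) will be used, as appropriate, with a fixed effect for randomized group", then "a random effect for school. The parameter of interest will be the log odds for the universal compared to the targeted screening group". It states no numerator or denominator, enrolment offset, weight, overdispersion term or grade-within-school term. School enrolment is collected under section 1.3, but 8.3 does not use it. On the amount of data, 8.3 says "we will have only 64 total data points (4 grades in each of the 14 schools", and it calls these analyses primarily hypothesis-generating. Section 7.2.2 randomizes grade levels within each school.

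**The concern.** A grade-level aggregate is not a binary outcome. To use logistic regression, the analyst must enter events out of students for each grade. With a school random effect only, students in a grade then count as independent given the school. The allocation was made to whole grades, so any real difference between grades of one school, apart from screening, belongs in the error of the treatment comparison. Leaving it out makes the standard error too small.

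The linear route raises a different question. On raw totals, the model ignores large differences in grade size, and the estimate is a difference in counts with no common meaning across grades. On rates, grade size enters as the denominator and only precision is given up.

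A linear model also yields a mean difference, so the log-odds parameter cannot apply to every outcome. The plan leaves the choice of route open for a question about unintended consequences, where a false alarm and a missed rise both matter.

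**Working it through.** **Stated row count.** 4 × 14 = 56, not 64. The figure 64 equals 4 × 16, which matches section 7.1: "3 schools will engage in the randomized control trial (RCT) in study year 1 and the additional 13 schools in study year 2" (3 + 13 = 16).

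**Grade sizes (section 8.1).** Rural: 3,900 / (9 × 4) = 108. Urban: 8,150 / (5 × 4) = 408 if there are 14 − 9 = 5 urban schools, which is an assumption. The ratio is 408 / 108 = 3.8. With 16 − 9 = 7 urban schools the urban figure is 8,150 / 28 = 291.

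**Assumptions not in the documents.** Event rate p of 5% or 10% (by symmetry also 95% or 90%); grade-within-school SD σ of 0 to 0.3 on the logit scale.

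**Approximation for the logistic route.** When the grade term is omitted, the true variance of the log odds ratio exceeds the model's by about

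D = 1 + m · p(1 − p) · σ², with m = Σn² / Σn over grade cells.

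Actual type I error is about 2[1 − Φ(1.96/√D)].

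With five urban schools, Σn² = 3,900²/36 + 8,150²/20 = 422,500 + 3,321,125 = 3,743,625. Then m = 3,743,625 / 12,050 = 310.7. For p = 10% and σ = 0.2, D = 1 + 310.7 × 0.09 × 0.04 = 2.12, 1.96/√2.12 = 1.35, and the error is 18%.

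**Simulation check.** 56 grade cells, 7:7 allocation of the two grade patterns, school SD 0.3 (assumed), 2,000 runs per setting, school fitted as a fixed effect in place of the random intercept.

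| p | σ | D | Formula | Simulated |
|---|---|---|---|---|
| 5% | 0 | 1.00 | 5% | 5.0% |
| 5% | 0.1 | 1.15 | 7% | 6.4% |
| 5% | 0.2 | 1.59 | 12% | 13.2% |
| 5% | 0.3 | 2.33 | 20% | 21.6% |
| 10% | 0 | 1.00 | 5% | 3.8% |
| 10% | 0.1 | 1.28 | 8% | 8.6% |
| 10% | 0.2 | 2.12 | 18% | 18.6% |
| 10% | 0.3 | 3.52 | 30% | 29.9% |

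A separate run gave 9-10%, 14-20% and 19-31% at σ = 0.1, 0.2 and 0.3. With seven urban schools, m = (422,500 + 8,150²/28) / 12,050 = 231.9, and the formula gives 6-8%, 10-15% and 17-25%.

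**Linear model on grade rates, unweighted.** In the same simulation, type I error was 4-6% throughout. Power for an odds ratio of 1.2 at a 10% rate was 0.71, 0.67, 0.52 and 0.38 at σ = 0, 0.1, 0.2 and 0.3, against 0.86, 0.78, 0.60 and 0.43 with size weights. The weighted model rejected a true null 4.3%, 5.8%, 7.2% and 7.9% of the time, so part of its gain at larger σ is looser error control.

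**Linear model on raw totals.** Type I error was also near 5%. Power at the 10% rate was 0.71 at σ = 0, equal to rates, but 0.29 against 0.38 at σ = 0.3. In a different scenario (0.25 violations per student, a 25% rise, grade SD 0.25 on the log scale; all assumed), power was 54% on totals and 71% on rates.

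**Partial remedies.** A binomial model with an overdispersion scale and a t reference still rejected 7-9% at σ = 0.2-0.3. If violations are repeat counts (mean 0.2 per student, strong clustering, both assumed), a Poisson model with an offset and no overdispersion rejected a true null 29-70% of the time. In the 0.25-per-student scenario, a negative binomial model with offset, random school and Wald test rejected 5% and 7.5% at grade SD 0.10 and 0.25. A binomial model with a school-by-grade random term was not simulated.

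**The case against.** The strongest reply is that section 8.3 already permits a sound analysis. A linear mixed model on grade rates treats the outcome as continuous, uses the grade as the unit, agrees with the sentence about having few data points, and holds its error near 5%. That stands, and it is the likelier reading of that sentence. The log-odds parameter points the other way, and the plan does not choose.

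A reader might go further and infer that every permitted model either ignores grade size or treats grade totals as independent students. The documents do not support that, because the model on rates does neither. A reader might also infer that violations are repeat counts with error of 26-54% under grouped logistic regression. Those figures come from an assumed 0.25 violations per student and grade SDs of 0.10-0.25, under the less likely reading, and the documents never state the recording scale.

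It is also fair to say that little hangs on this. The analyses are labelled hypothesis-generating, sections 1.1 and 1.3 warn that the data may be unavailable after the COVID-19 closures, and advancement/graduation is now a listed endpoint, not a numbered hypothesis. For the hypothesis of no change in violations, the missing equivalence margin is a separate gap that no choice of model repairs.

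**Conclusion.** The point holds in limited form. If advancement or graduation is analysed by logistic regression on grade totals with a school effect only, the test is too liberal: about 6-10% at a grade SD of 0.1, 13-20% at 0.2 and 19-31% at 0.3, against a nominal 5%. This rests on assumed SDs, on event rates of 5-10% and on five urban schools; seven would lower the figures somewhat. With no variation between grades of a school, the error is nominal.

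A linear model on raw totals ignores a roughly fourfold difference in grade size under the same five-school assumption. That costs power in some settings and does not raise the error. A linear model on rates is valid, with some loss of power. Calling the parameter a log odds for every outcome is wrong for any linear model. The secondary, exploratory status of these analyses keeps this a low-priority correction.

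**What to change.** In section 8.3, specify for each Objective 2 outcome:

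- **Data.** Obtain the numerator and the grade enrolment with every aggregate, and state the recording scale. Section 7.2.1 assigns every student in grades 9-12, opt-outs included, a study ID that carries the grade, so enrolment can be counted from the linking lists. Total grade enrolment is the matching denominator, since 8.3 notes that aggregates include students outside the study.
- **Advancement/graduation.** Events out of students with a school-by-grade random term, or an unweighted linear model on grade rates.
- **Violations/suspensions and missed days.** Rates per enrolled student or, if supplied as counts, a negative binomial model with log enrolment as offset.
- **Inference.** Small-sample t inference throughout. Pair any size weighting with a grade-level variance term, because weights alone ran above 5%.
- **Effect measure.** Rate ratio, odds ratio or mean difference, as the model gives, in place of a log odds throughout.
- **Row count.** Reconcile 64 with 4 × 14 = 56.

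The cost is protocol wording, one extra column in the district file, and slightly more complex models on 56 rows for exploratory analyses.
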